5 SAMPLE SIZE AND POWER

This study is descriptive in nature and is not powered to show statistically significant treatment differences for any outcome measure. A sample of approximately 70 subjects, randomized in a 1:1 ratio to the belatacept + EVL and TAC + MMF groups, is planned.

If the true probability of CSBPAR in the belatacept + EVL treatment group is 3.8%, a sample size of 35 subjects allows the estimation of the population proportion (π) with a 95% CI[†] of 0.2% to 16.4% around the observed proportion of CSBPAR. If the rate is 3%, in the TAC +MMF treatment group, then the 95% CI[†] around the estimate would be 0.1% to 15.1%, for lower and upper limits, respectively.

For the secondary endpoint of assessing the difference in the incidence of CSBPAR at 6 months post-transplantation between the TAC + MMF and belatacept + EVL groups, respectively, with 35 subjects per treatment group, if the observed incidences of CSBPAR (conservatively based on study IM103034) are 3% and 3.8%, the 2-sided 95% confidence interval (CI)* of the differences between the observed incidence rates can be summarized as in Table 5-1:

Table 5-1: Confidence Intervals* for the Difference between Two Proportions

Difference of Treatments (assumed proportions)	Lower 95% Confidence Limit	Upper 95% Confidence Limit	Half Width
TAC + MMF (3%)			
vs.	-13.2%	11.3%	12.25%
Bela + EVL (3.8%)			

[†] Confidence Interval Method: Clopper-Pearson

* Confidence Interval Method Score (Wilson)

6 STUDY PERIODS, TREATMENT REGIMENS AND POPULATIONS FOR ANALYSES

6.1 Treatment Regimens

Approximately 70 subjects (n=35 per arm) receiving de novo kidney transplants will be randomized (stratified by study site/center) in a 1:1 ratio to 1 of the following 2 treatment groups:

- Thymoglobulin + Belatacept + Everolimus.
- Thymoglobulin + Tacrolimus + MMF.

6.2 Populations for Analyses

- The “Intent-to-Treat” (ITT) population includes all subjects who are randomized, transplanted and treated with at least one dose of thymoglobulin and one dose of study treatment, either belatacept or TAC. Subjects will be grouped according to the treatment to which they are randomized.
- The “As Treated” (AT) population includes all subjects who are randomized, transplanted and treated with at least one dose of thymoglobulin and one dose of study drug, either belatacept or TAC. Subjects will be grouped according to the treatment which they actually received. The “As Treated” treatment group is the same as the “As Randomized” treatment group, except in cases where a subject received a different treatment from the one he/she was randomized to for the entire course of their participation in the study. In this case, the “As Treated” treatment group is set to the treatment the subject actually received. In cases where a subject received different treatments after randomization, then the “As Treated” treatment group is the first treatment received. Safety reporting will be done in the “As Treated” population.
- The “Per-Protocol” (PP) population includes all randomized subjects who do not violate terms of the protocol that might affect key study outcomes. The protocol specific definitions for “relevant” protocol deviations are described in [APPENDIX 2](#).
- The PK population includes subjects who receive at least one dose of belatacept and have at least 1 post baseline sample available for PK analyses.

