## 8.2 Populations for Analyses

- The primary endpoint will be initially assessed on the ITT population in each treatment group. The ITT population will consist of all randomized and transplanted subjects treated with at least one dose of Thymoglobulin and one dose of study treatment, either belatacept or TAC, and will be included in the safety and efficacy analysis data sets. In these analyses, CSBPARs occurring after discontinuation from assigned therapy will be counted in the treatment arm to which the subject was originally randomized.
- Additionally, for CSBPAR, a sensitivity analysis will be performed with right censoring at the time of discontinuation from the assigned therapy.
- An as-treated analysis will be based on the treatment regimen received. Analysis of treatment differences in the rates of CSBPAR will only include those subjects who remain on their original therapy from the beginning, through the designated analysis time point(s) (e.g., the Months 6, 12 and 24 study visits) for these above mentioned analyses. Treatment differences in the rates of CSBPAR will also be performed using a per protocol efficacy dataset.
  - This is defined as the set of all data derived from that subset of subjects once treated, are followed up consistently with all study criteria to the extent that no relevant protocol deviations have been identified.

The primary analysis will be done on the ITT population and the sensitivity analyses on the primary endpoints will be done in the As Treated, as well as the Per Protocol population.

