2.2 Treatment Assignment

Approximately 70 subjects (n=35 per group) receiving *de novo* kidney transplants from living or standard criteria deceased donors, were to be randomized (stratified by study site/center), in a 1:1 ratio, to one of the 2 specified treatments groups. A randomization schedule was to be generated and kept by BMS.

At the time of enrollment, immediately after written informed consent was obtained, and before performing any study-specific procedures, the physician/coordinator was to contact IVRS to enroll each subject into the centralized database. Each subject was to be assigned a unique, sequential, 5-digit subject number beginning with 80001, 80002, 80003, etc. by the interactive voice response system (IVRS) for identification throughout the study. This subject number was not to be reused for any other participant in the study. SAE reporting was to begin at the time of enrollment for all subjects, immediately after written informed consent was obtained.

The subject could be randomized once all entry criteria (inclusion and exclusion) had been met. The physician/coordinator was to contact IVRS prior to transplant surgery to randomize each subject into the centralized database. The collection of non serious AE information was to begin at initiation of study drug. The IVRS was also to be contacted at each visit to obtain belatacept vial assignments and each time additional supplies of other investigational products were to be dispensed.

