7.3 Study Conduct

All subjects with relevant protocol deviations that could affect efficacy will be identified. A list of these protocol deviation criteria is provided in [APPENDIX 2](#). These protocol deviations are referred to as “relevant” protocol deviations in this document.

All randomized subjects with at least one relevant protocol deviation will be summarized by treatment group and overall. They will also be listed.

The ITT analysis population will be used for these analyses.

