7.4 Extent of Exposure

7.4.1 Subject Disposition

The disposition of subjects will be presented as follows:

- Number of subjects enrolled at screening.
- Number of subjects randomized and transplanted, presented by randomized treatment group.
- Reasons for not being randomized.
- Number of randomized and transplanted subjects who receive at least 1 dose of Thymoglobulin and 1 dose of study treatment, either belatacept or TAC.
- Number of subjects who discontinued treatment at any time during the two years, together with reasons for discontinuation, as tabulated by randomized treatment group.
- Number of subjects continuing in the follow up phase.
- Number of subjects who discontinued study during the follow up phase, together with reasons for discontinuation and tabulated by randomized treatment group.

For the items above, the overall disposition combining all treatment groups will also be presented.

A corresponding listing of subjects who discontinued from the treatment period (including subjects randomized but not treated) and the follow up period will be provided, together with the reason for discontinuation.

The ITT analysis population will be used for these analyses.

Enrollment at each site and by age group will be summarized as specified in EudraCT requirements.

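### The 'ITT' set is a modified ITT with no wider check, the SAP 7.4.1 disposition is run on a set that cannot hold all its rows, and the SAP per-protocol base departs undeclared from protocol 8.2

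*SAP*

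**What the plan says.** **ITT.** SAP 6.2 requires subjects to be "randomized, transplanted and treated with at least one dose of thymoglobulin and one dose of study treatment, either belatacept or TAC". Protocol 8.2 has the same rule: "all randomized and transplanted subjects treated with at least one dose of Thymoglobulin and one dose of study treatment", again belatacept or TAC. Subjects are analysed as randomized.

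**As-Treated.** SAP 6.2 gives the same entry rule: it "includes all subjects who are randomized, transplanted and treated with at least one dose of thymoglobulin and one dose of study drug". Only the grouping differs.

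**Timing.** SAP 2.2: "The physician/coordinator was to contact IVRS prior to transplant surgery to randomize each" subject. Protocol 4.2 agrees, and protocol 4.4 confirms open-label treatment.

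**Outputs assigned to ITT.**
- SAP 7.4.1 (disposition) asks for the number enrolled at screening, "Reasons for not being randomized", and a discontinuation listing that takes in randomized subjects who were never treated. It then names ITT for all of it.
- SAP 7.3: "All randomized subjects with at least one relevant protocol deviation will be summarized by treatment group and overall". It also names ITT.
- SAP 7.4.2 treats all randomized subjects and the ITT population as one set. Protocol 8.4.1 says only ITT.

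**Per-protocol.** In SAP 6.2 this "population includes all randomized subjects who do not violate terms of the protocol that might affect key study outcomes", with the deviations given in Appendix 2. Protocol 8.2 starts instead from the "subset of subjects once treated, are followed up consistently with all study criteria", without relevant deviations. On per-protocol, SAP 7.1 declares only that the analysis runs if at least 10% of either group have a deviation.

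**The concern.** An intention-to-treat set normally depends only on randomization. Leaving out subjects who were never transplanted is easy to defend here, since they have no graft to reject. Leaving out transplanted subjects who got no Thymoglobulin, or neither belatacept nor TAC, is different: it depends on events after assignment, under open-label conditions.

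The time at risk before the qualifying dose can also differ by arm. Protocol 4.3.1 starts belatacept 12 to 24 hours after the first Thymoglobulin infusion ends. Protocol 4.3.5 lets TAC start within 24 hours of transplant or be delayed up to Day 7. A late start does not itself exclude anyone, and neither does receiving the other arm's drug. The subjects at issue are mainly very early failures and subjects given a regimen with neither drug.

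Three things follow:
- No planned summary is sure to include these subjects, because As-Treated shares the rule and per-protocol is conditional.
- A disposition table restricted to ITT cannot show how many were left out, from which arm, or why.
- A per-protocol set built on all randomized subjects need not be a subset of ITT, and could contain someone with no graft.

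**Working it through.** **1. The plan's own figures (SAP 5, 35 per group, 3.8% belatacept + EVL, 3% TAC + MMF).** Expected events are 35 × 0.038 = 1.33 and 35 × 0.03 = 1.05. Clopper-Pearson limits for x events in n are the 2.5% quantile of Beta(x, n − x + 1) and the 97.5% quantile of Beta(x + 1, n − x).

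| Quantity | Recomputed | SAP |
|---|---|---|
| 3.8%, n = 35 | 0.21% to 16.37% | 0.2% to 16.4% |
| 3%, n = 35 | 0.09% to 15.14% | 0.1% to 15.1% |
| Difference 3% − 3.8% (two Wilson intervals combined, Newcombe) | −13.17% to 11.32% | −13.2% to 11.3% |

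The SAP figures reproduce. They take all 35 per group as analysed.

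**2. Each output against the ITT conditions.**

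| Output | Can it lie in the ITT set? |
|---|---|
| 7.4.1 screened subjects; reasons for non-randomization | Not beyond those later randomized and dosed |
| 7.4.1 randomized, untreated subjects | No |
| 7.4.1 count transplanted, and count also dosed | Yes, but the two are equal by definition |
| 7.3 deviations | Yes; only the phrase about all randomized subjects is wrong |
| 7.4.2 baseline | Yes; only the equation of the two sets is wrong |

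**3. Likely effect on rejection.** Assume k = 1 or 2 excluded per arm (the documents give no number; k = 0 is possible), all rejection-free. The proportion moves from x/35 to x/(35 − k).

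| x | k = 0 | k = 1 | k = 2 |
|---|---|---|---|
| 1 | 2.86% | 2.94% (+0.08) | 3.03% (+0.17) |
| 2 | 5.71% | 5.88% (+0.17) | 6.06% (+0.35) |

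At the plan's rates, one to four excluded subjects in total carry between 1 × 0.03 = 0.03 and 2 × 0.03 + 2 × 0.038 = 0.14 expected rejections.

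**4. Constructed worst case.** One excluded subject had a rejection. The arm goes from 2/35 = 5.7% (Clopper-Pearson 0.7% to 19.2%) to 1/34 = 2.9% (0.1% to 15.3%). Against 1/35 in the other arm, the difference goes from +2.9 points (−9.5 to 16.0) to +0.1 (−11.8 to 12.3). The intervals overlap widely.

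**5. Survival.** If one of five deaths or graft losses is in a never-dosed subject, 5/70 = 7.1% becomes 4/69 = 5.8%. SAP 7.6.2.1 produces its summaries only from five such subjects upward and names no counting set.

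**6. Per-protocol.** The trigger is 10% of 35 = 3.5, so four subjects (4/35 = 11.4%; 3/35 = 8.6% falls short). Suppose four deviators without events are removed, leaving 31, of whom one or two were never transplanted and are scored rejection-free. Compared with leaving them out, the proportion is lower by 1/30 − 1/31 = 0.11 points (x = 1, one subject) up to 2/29 − 2/31 = 0.45 points (x = 2, two subjects). Appendix 2 code 6 may catch undosed subjects given another treatment; no code clearly removes a never-transplanted one.

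**The case against.** The other side has a good deal that stands.

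- **Label.** Both documents spell out the ITT set identically, so there is no protocol-SAP conflict and membership is not hidden. Calling it ITT is a labelling matter.
- **Hidden cases.** A reader might infer that an excluded rejection, death or graft loss would vanish. The text does not support this. SAP 7.6.1.1 lists all suspected rejections whenever they occurred, SAP 7.6.2.1 lists all deaths and graft losses, and neither listing is limited to ITT.
- **SAP 7.3 and 7.4.2.** A reader might infer that these tables cannot be produced. They can; only a phrase in each is wrong. In 7.4.1 the itemised rows show what was meant, but the closing sentence contradicts them.
- **Five-event trigger.** A reader might infer that it would be missed. In SAP 7.1 and 7.6.2.1 it follows a listing of all subjects who died or lost a graft, so counting in the wider set is at least as natural. It is unstated rather than wrong.
- **Rejection-free scoring in per-protocol.** SAP 8.3 could score a never-transplanted subject as rejection-free, but SAP 8.4 counts from the first dose, so a wholly undosed subject has no Day 1. The outcome is unclear, not established.
- **Undeclared change.** One Section 6 item in the SAP document history is redacted, so a note there cannot be ruled out. SAP 7.1, where departures are declared, is readable and silent.

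What remains is the absence of any wider planned summary, the 7.4.1 contradiction, and the changed per-protocol base.

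**Conclusion.** The concern holds as a minor point. The primary set is a modified ITT whose membership depends on post-randomization events, and As-Treated cannot check it. SAP 7.4.1 contradicts itself on population. The SAP per-protocol base differs from protocol 8.2 without declaration in SAP 7.1.

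The likely effect on the rejection proportion is below 0.4 points, against a planned half-width of 12.25 points for the difference. This assumes no more than two exclusions per arm, all rejection-free. The number and direction are unknown, and no one may be affected. The documents do not show that any result is biased; the worst case above is constructed. The study is descriptive, so no error rate or power figure changes.

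**What to change.** 1. **Keep the dosed set as primary, described in the SAP as modified ITT.** Add one sensitivity analysis of CSBPAR and of subject and graft survival in all randomized, transplanted subjects, as randomized. State that the five-event trigger is counted in that set. For undosed subjects, set Day 1 in SAP 8.4 to the transplant date so that they have a counting period.
2. **Define per-protocol as a subset of the transplanted and treated set**, in line with protocol 8.2.
3. **Run the SAP 7.4.1 disposition on all enrolled or randomized subjects**, with exclusions from the dosed set by arm and reason. Correct the phrases on all randomized subjects in SAP 7.3 and 7.4.2.

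**Cost.** One extra table and wording in SAP 6.2, 7.1, 7.3, 7.4.1, 7.4.2, 7.6.1.1, 7.6.2.1 and 8.4. No new survival data are needed: protocol 6.1.1 already requires deaths and graft losses to be reported for all randomized subjects. Renaming the set in protocol 8.2 would be a protocol revision and is not needed.

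**Downside.** The documents do not state how undosed subjects are followed for rejection, so some may count as rejection-free in the added analysis. List them individually beside it.

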7 STATISTICAL ANALYSES

7.1 Modifications to the Analyses Specified in the Protocol

Due to the reduction in sample size resulting from premature termination of enrollment as of 31 December 2016, it has been deemed appropriate to revise selected statistical analyses specified in the study protocol [Section 8](#). The following modifications to and clarifications of the analyses have been made:

- 1) All analyses will be performed for the whole study treatment period (i.e. 24 months), including analyses at 6 or 12 months.

- 2) Treatment differences will be produced only for the endpoints specified in the sections of this SAP itemized below, instead for all study endpoints.
- 3) Analysis of acute rejections:
 - a) The treatment differences in the severity grades and therapeutic modalities will not be calculated.
 - b) The sensitivity analyses using the per-protocol population will be performed if there are at least 10% of subjects with a protocol deviation in either treatment groups.
 - c) The sensitivity analyses using the as-treated population will be performed if there are at least 10% of subjects in either treatment group for whom the as-randomized treatment group is different from the as-treated treatment group.
 - d) The sensitivity analysis using right censoring at the time of discontinuation from assigned therapy will not be produced. Acute rejections occurring more than 56 days after the last dose date will be flagged in the listing.
 - e) The descriptive summaries by treatment group for cGFR, graft and subject survival, donor specified antibodies, infection and malignancy at Month 12 for subjects with and without AR by Month 6, and at Month 24 in subjects with and without AR by Month 12, will not be produced. The information regarding these parameters will be included in listings that correspond to the specific analyses of these endpoints.
- 4) Analysis of subject and graft survival:
 - a) A listing including all subjects who died or lost their graft will be produced. Corresponding summaries, treatment differences and time to event analysis will be produced if there are at least 5 subjects across treatment groups who died or experienced graft loss during the 24 Month treatment period.
 - b) Any summaries mentioned above, if to be produced, will only be produced for the whole 24 Month treatment period. The corresponding analyses at 6 and 12 months will not be produced.
 - c) Subject and allograft survival rates among those subjects who did and those who did not experience CSBPAR. This analysis will be produced only if there are at least 5 subjects across treatment groups who died or experienced graft loss during the 24 month-treatment period.
- 5) Analysis of the composite endpoints of CSBPAR, death, or graft loss will be produced only if there is at least one CSBPAR and at least one death or graft loss. These analyses will include the proportion of all subjects who experience CSBPAR, death, or graft loss at 12 and 24 months and a time to event analysis of the composite endpoint of CSBPAR, death, or graft loss.
- 6) All safety analyses will only be produced for the whole 24 Month treatment period. The corresponding safety analyses at 6 and 12 months will not be produced.
- 7) Analysis of immunogenicity: The protocol specifies summaries of titers of detectable anti-belatacept antibodies at Weeks 8, 12, and 24 post study termination (subjects who discontinue belatacept only). Instead of descriptive statistics, a listing will be provided for all positive subjects. Similarly, the analysis of descriptive statistics for titers of detectable anti-belatacept antibody will not be produced.

- 8) Analysis of any clinical consequences of CSBPAR (and associated changes in the expression of exploratory gene sets associated with acute rejection) at 6, 12 and 24 months post-transplant will be presented as follow:
 - a) The extent to which renal function recovered to the pre-rejection baseline will include the serum creatinine values related to CSBPAR in the corresponding listing.
 - b) The percentage of subjects who, post-CSBPAR, are reported to have developed infection or malignancy will not be summarized. Instead, a listing will be provided.
 - c) The percentage of subjects with, and titers of detectable, de novo (post-transplant) anti-belatacept antibodies will not be summarized. Instead, this information will be included in a listing of immunogenicity results with corresponding belatacept concentrations and selected laboratory parameters and events of special interest.
 - d) The subject and graft survival rates among those subjects who did, and those who did not experience CSBPAR will be provided only if there are at least 5 subjects across treatment groups who died or experienced graft loss during the 24 month-treatment period.
- 9) The summary of median fluorescence intensity (MFI) of anti-HLA donor specific antibodies will not be produced. Instead, the number of subjects with DSA will be summarized.
- 10) Analysis of anti-viral T-cell responses will not be provided. The immune cell phenotypes will be summarized for all subjects and by acute rejection status (subjects experiencing at least one acute rejection vs those without any acute rejection). A corresponding listing will be provided.
- 11) The patterns of protein excretion, by urinary proteomics will be summarized for all subjects and by acute rejection status (subjects experiencing at least one acute rejection vs those without any acute rejection). Proteins that are below LLOQ in more than 50% of samples will not be analyzed. A corresponding listing will be provided.

Due to the fact that some data were not collected, the following analyses cannot be produced:

- 1) Clinically significant changes in vital signs were not collected. Thus, they will not be summarized. Instead, a summary of the number of subjects with systolic or diastolic blood pressure values above the values mentioned in [section 7.6.2.5](#) will be provided. Also, investigators may have reported corresponding adverse events which will be summarized and listed as described in [Section 7.7](#).
- 2) For the analysis of any clinical consequences of CSBPAR, and associated changes in the expression of exploratory gene sets associated with acute rejection, no summary or listing that includes gene expression will be provided.
- 3) The analysis on titers of DSA and of the characterization of any de novo DSA detected by IgM and IgG classes, and by the presence or absence of complement fixing properties will not be produced. Instead, the number of subjects with DSA will be summarized.
- 4) The IHC analyses of any remaining allograft biopsy tissue samples available at sites following clinical review will not be provided, as no such residual tissue samples were submitted for this purpose.

The following analyses will not be provided as part of this analysis plan:

- 1) The analyses related to anti-viral T-cell responses and mean percent change in anti-viral T cell responses will not be produced as part of the analyses described in this analysis plan. If they are to be performed subsequently, they will be described in a separate analysis plan.
- 2) The analyses of peripheral blood and urinary (mRNA) gene expression profiles will not be produced as part of the analyses described in this analysis plan. If they are to be performed subsequently, they will be described in a separate analysis plan.
- 3) The analyses of gene expression profile, plasma and urine samples for the global and targeted quantitative determination of proteins in plasma and urine and unstained sections of allograft biopsy tissue will not be produced as part of the analyses described in this analysis plan. If they are to be performed subsequently, they will be described in a separate analysis plan.
- 4) The analyses related to the study endpoint to explore the exposure response relationships for selected safety, efficacy, and biomarker endpoints in each treatment group will not be described in this analysis plan. If they are to be performed subsequently, they will be described in a separate analysis plan.

The following clarifications to the study endpoints of the analyses are listed below:

- 1) The “description” of clinically significant changes in vital signs and of laboratory test marked abnormalities, as mentioned in the study endpoints (see [Section 4.2](#)) refers to descriptive statistics.
- 2) Analysis of vital signs: The protocol Section 8.4.2.5 specifies the analyses related to cardiovascular and metabolic co-morbidities as part of the efficacy analyses. These also include the summaries over time of systolic and diastolic blood pressures. In order to maintain consistency, the descriptive analysis of all vital signs over time will follow the same conventions as those for the efficacy endpoints, despite being mentioned as a safety endpoint in this analysis plan.

